## Intent to Treat (ITT) Population

The intent-to-treat (ITT) population consists of each eligible and randomized study subject who received control and test implants in two different quadrants and from whom at least one follow-up measurement after placement is available. This population will include subjects regardless of any protocol deviations (e.g. implant loss of study control or study test implant and/ or premature termination).

The study control and study test implant of the ITT population will be the basis for the implant survival analysis.

#### Per-Protocol (PP) Population

The per protocol (PP) population consists of each eligible study subject with one study control and one study test implant and who performed all follow-up visits according to the study protocol. Subjects with major protocol deviations (as defined in 11.4.1) will be excluded from this population. In the occurrence of a study control or study test implant loss the patient will be excluded from the PP population. Exclusion of subjects with minor protocol deviations will be determined on a case-by-case basis.

The primary effectiveness analysis will be based on the PP population.

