# Secondary effectiveness analysis

The secondary endpoints as listed in Section 3.4.2 will be compared between the treatment groups for the time points recorded (Table 2). Comparisons between the treatment groups will be based on 95% confidence intervals.

Beyond the secondary endpoints in the secondary hypotheses, all stated quantitative secondary endpoints should be analyzed using repeated measures modeling. This will control for any effects expected to be significant. The response and/or explanatory variables may need to be transformed depending on their ability to meet the assumptions of the model.

Through using repeated measures modeling and the randomization scheme proposed we may disregard any specific implant within quadrant randomization and the need to limit measure comparisons between two implants alone. This maintains result integrity by including all information in the analysis. Furthermore, secondary variables that have measures across more than two time-points are analyzed with these methods with no loss in data.

The survival analysis will be carried out over the study implants (study control and study test implant) placed at the surgery visit (V2) and within the ITT population. Implant survival will be analyzed using the Kaplan-Meier Survival estimate with Confidence Intervals (CI) given by the Greenwood formula. Considering that for this study the number of patients not completing the 12 months follow-up visit may exceed 5% due to missed follow-up visits, the formula of Rothman will used for confidence intervals.

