## 9.4 Sample size

The primary hypothesis is that 12 months after loading, the marginal bone loss around the SLActive® implants will not be appreciably greater than around the SLA® implants.

In the case of MBL, where smaller values are better, the null and alternative hypotheses can be stated as follows:

 $H_0$ : Mean MBL for the test >= Mean MBL for the control + tolerance range  $H_A$ : Mean MBL for the test < Mean MBL for the control + tolerance range

The tolerance range or non-inferiority margin characterizes the largest absolute difference which is considered to be dismissible. A MBL of less than 0.5mm within the first year after implant loading constitutes an acceptable clinical standard (28, 45, 46). In this clinical trial, a non-inferiority margin of 20% of the acceptable clinical standard was chosen, which amounts to 0.1mm.

Based on Karabuda et al (28) who compared MBL in SLActive® and SLA® implants one year after loading, if it is assumed that the mean and SD would be  $0.46 \text{mm} \pm 0.20 \text{mm}$  for SLA® and for the scenario of  $0.43 \text{mm} \pm 0.22 \text{mm}$  for the SLActive® (with a correlation=0.0), that a difference of 0.10 mm or less is unimportant and that the alpha (one tailed) is set to 0.05, then with a sample size of 51 patients (51 pairs, a pair within a patient), the study will have a power of 92.4% to show that the mean MBL for the SLActive® surface is at least as low as the mean for the SLA®. The null hypothesis is then, that the mean for the SLActive® is 0.10 mm higher than the mean for the SLA®, and that the study has a power of 92.4% to reject this null hypothesis.

The Proc Power procedure of the software SAS v9.4, SAS Institute AG, Cary NC USA was used for calculations

60 patients will be enrolled in order to take into account a 20% dropout rate.

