## a) Major protocol deviation:

- Increases risk to one or more participants;
- Adversely affects the safety, rights or welfare of one or more participants; or
- Adversely affects the integrity of the study.

Examples of major protocol deviations include: Informed consent obtained after the initiation of study procedures, failure to report a SAE, deviation from inclusion/exclusion criteria, deviation from withdrawal criteria (section 3.7.3), loading of the study control or study test implant not performed at the loading visit

b) Minor protocol deviation is a contravention of the protocol that does not impact participant's safety, nor compromises the integrity of the study data, neither/nor ethics of the study. Note: Several minor observations may collectively be considered as equal to a major protocol deviation.

Examples: Delay in performing study procedure (i.e., time window deviation).

Placement of study devices not according to randomization will be discussed on a case by case basis (e.g. assessment from the clinician of the clinical situation in the quadrant where the implants were placed compared to the randomized quadrant).

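### The primary (per-protocol) set is defined by attendance at every follow-up visit, so on its literal wording it can discard pairs whose bone-level radiographs are complete; the likely power loss is modest and the remedy is one clause.

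*Combined protocol and SAP*

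**What the plan says.** Section 9.3 defines the PP population as eligible patients with one test and one control study implant "who performed all follow-up visits according to the study protocol". Two further rules remove patients: major deviations as defined in section 11.4.1, and loss of a study implant ("In the occurrence of a study control or study test implant loss the patient will be excluded from the PP population"). A third leaves room for judgement: "Exclusion of subjects with minor protocol deviations will be determined on a case-by-case basis". The section then states: "The primary effectiveness analysis will be based on the PP population".

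Table 2 (section 6) marks peri-apical radiographs at Visit 2 (placement), Visit 7 (loading) and Visit 9 (12 months). Visits 3, 4, 5, 6 and 8 have none.

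Section 11.4.1 gives one kind of example of a minor deviation, a procedure carried out late or outside its window. It does not classify a visit that is missed altogether. Section 9.1 leaves the assessment of deviations to a data review meeting and rules out imputation of primary and secondary outcomes. Section 9.3 names the ITT population as the basis for implant survival; no ITT analysis of bone level is stated.

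**The concern.** The condition for entering the primary analysis is wider than the data the analysis needs. Bone-level change requires two radiographs per implant. Visits 3 to 5 serve fluid sampling, bacterial sampling and wound healing. Visit 8 records survival, prosthetic status and safety. Missing one of these leaves the primary endpoint untouched, yet the definition as written removes the patient.

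Because the design is paired within patient, such an exclusion removes one test and one control implant together. The direct cost is therefore precision and power, not imbalance between the surfaces. The second cost is that, if discretion is used to keep such patients, membership of the primary non-inferiority set is settled at a meeting without a pre-specified rule.

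**Working it through.** **Inputs (section 9.4).** Control mean 0.46 mm, SD 0.20; test mean 0.43 mm, SD 0.22; within-pair correlation 0; "a non-inferiority margin of 20% of the acceptable clinical standard was chosen, which amounts to 0.1mm"; "the alpha (one tailed) is set to 0.05"; 51 pairs; 60 patients enrolled; 20% dropout.

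**Step 1: reproduce the stated power.**
- SD of the paired difference = √(0.20² + 0.22²) = √0.0884 = 0.297 mm.
- Distance from the assumed difference to the margin = 0.10 − (0.43 − 0.46) = 0.13 mm.
- Noncentrality at n = 51: 0.13 / (0.297/√51) = 3.12, with 50 degrees of freedom.
- Power from the noncentral t distribution, one-sided 0.05: 92.4%. This matches the plan.

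**Step 2: power by number of evaluable pairs, same method.**

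| Pairs | 51 | 48 | 47 | 46 | 44 | 42 | 41 | 39 | 34 | 33 |
|---|---|---|---|---|---|---|---|---|---|---|
| Power (%) | 92.4 | 91.0 | 90.5 | 89.9 | 88.7 | 87.3 | 86.6 | 85.0 | 80.3 | 79.2 |

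**Step 3: the surplus.** 60 − 51 = 9 patients, and 9/60 = 15%. A true 20% dropout leaves 60 × 0.80 = 48 pairs, already below 51, before any pair is lost to the visit clause.

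**Step 4: pairs lost only through the visit clause.** Visits 3, 4, 5 and 8 are counted. Visit 6 is left out because its torque check decides whether the implant can be loaded at Visit 7 (sections 6.7 and 7.2.4), and non-loading at the loading visit is already a major deviation (section 11.4.1). The documents give no rate for missed interim visits, so 2% and 5% per visit, independent across visits, are assumptions. The share kept is 0.98⁴ = 0.922 or 0.95⁴ = 0.815.

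| Start | Missed per visit | Pairs left | Power |
|---|---|---|---|
| 51 | 2% | 51 × 0.922 = 47.0 | about 90.5% |
| 51 | 5% | 51 × 0.815 = 41.5 | about 87.0% |
| 48 | 2% | 48 × 0.922 = 44.3 | about 88.8% |
| 48 | 5% | 48 × 0.815 = 39.1 | about 85.1% |

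**Step 5: sensitivity to the other assumptions.** With a within-pair correlation of 0.3, 48 pairs give 97.3% and 40 pairs 94.5%. With a true difference of zero instead of 0.03 mm in favour of the test surface, 51 pairs give 76.6%, 48 give 74.3% and 39 give 66.2%. The cost of lost pairs is smaller in the first case and larger in the second.

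**The case against.** The strongest reply is that exclusion is not certain. The case-by-case sentence stands in the same section, section 11.4.1 defines a minor deviation as one that harms neither safety nor data integrity, and section 9.1 makes only major deviations an automatic exclusion. A skipped 2-week visit with complete radiographs could well be judged minor and the patient kept. This stands: a reader might infer that one missed visit always drops a pair, and the documents do not support that. It does not clear the text, because attendance is written as a condition of membership, the discretion concerns exclusion for minor deviations, and no section says which class a missed visit falls in.

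Three other stronger readings also fail:

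- **That the plan itself forecasts missed interim visits.** Section 9.2 does say that "the number of patients not completing the 12 months follow-up visit may exceed 5% due to missed follow-up visits", but this concerns the 12-month visit and serves the choice of a survival confidence interval. Those patients lack the Visit 9 radiograph and would be lost under any definition.
- **That five visits are at issue.** Counting Visit 6 as well would give 51 × 0.98⁵ = 46.1 or 51 × 0.95⁵ = 39.5 pairs (90.0% or 85.4%). But a patient who truly misses Visit 6 is likely to leave the PP set through the loading rule anyway.
- **That the trial will fall below 51 pairs or be underpowered.** Power drops below the stated figure only once the surplus of 9 is used. With no dropout at all, 2% missed per visit would leave 60 × 0.922 = 55.3 pairs. Section 3.7.3 also lets non-attenders be withdrawn, and withdrawn patients are replaced while recruitment is open. Section 9.4 states no minimum power, and power stays above 80% down to 34 pairs.

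Finally, section 9.2 refers to the SAP for detail. No separate SAP text is included in the supplied document, so whether it settles the matter cannot be judged.

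**Conclusion.** The point holds in a limited form. As written, the primary set can leave out pairs with complete primary-endpoint data, or keep them only by a decision for which no rule is given, and the supplied text offers no other bone-level analysis that would use them. On assumed independent miss rates of 2% to 5% at each of Visits 3, 4, 5 and 8, the clause costs about 2 to 5 points of power from 51 pairs (92.4% to between 90.5% and 87.0%) and about 2 to 6 points from 48 (91.0% to between 88.8% and 85.1%). These figures also assume that the surplus is spent, that nobody is kept by discretion, and that the section 9.4 means, SDs and zero correlation hold. The loss is modest, but it is avoidable, and the missing rule should be written down whatever the attendance turns out to be.

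**What to change.** For the primary bone-level analysis, replace the attendance clause in section 9.3, and the matching SAP text, with:

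> Has evaluable peri-apical radiographs of both study implants at the start visit of the primary endpoint and at Visit 9. Missing Visit 3, 4, 5 or 8 alone does not exclude a patient.

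The start visit should be named, since section 3.4.1 does not say whether change is counted from placement or from loading. Keep the existing major-deviation exclusions, including non-loading at the loading visit, so that a missed Visit 6 is judged by those rules and not by an attendance rule.

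The cost is one clause in each document, with no new data or visits. The drawback is that the primary set is no longer fully visit-compliant; keeping the present all-visits PP set as a sensitivity analysis covers this.

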## 9.4 Sample size

The primary hypothesis is that 12 months after loading, the marginal bone loss around the SLActive® implants will not be appreciably greater than around the SLA® implants.

In the case of MBL, where smaller values are better, the null and alternative hypotheses can be stated as follows:

 $H_0$ : Mean MBL for the test >= Mean MBL for the control + tolerance range  $H_A$ : Mean MBL for the test < Mean MBL for the control + tolerance range

The tolerance range or non-inferiority margin characterizes the largest absolute difference which is considered to be dismissible. A MBL of less than 0.5mm within the first year after implant loading constitutes an acceptable clinical standard (28, 45, 46). In this clinical trial, a non-inferiority margin of 20% of the acceptable clinical standard was chosen, which amounts to 0.1mm.

Based on Karabuda et al (28) who compared MBL in SLActive® and SLA® implants one year after loading, if it is assumed that the mean and SD would be  $0.46 \text{mm} \pm 0.20 \text{mm}$  for SLA® and for the scenario of  $0.43 \text{mm} \pm 0.22 \text{mm}$  for the SLActive® (with a correlation=0.0), that a difference of 0.10 mm or less is unimportant and that the alpha (one tailed) is set to 0.05, then with a sample size of 51 patients (51 pairs, a pair within a patient), the study will have a power of 92.4% to show that the mean MBL for the SLActive® surface is at least as low as the mean for the SLA®. The null hypothesis is then, that the mean for the SLActive® is 0.10 mm higher than the mean for the SLA®, and that the study has a power of 92.4% to reject this null hypothesis.

The Proc Power procedure of the software SAS v9.4, SAS Institute AG, Cary NC USA was used for calculations

60 patients will be enrolled in order to take into account a 20% dropout rate.

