# 3.6 Study Duration

The first patient was enrolled in the study in October 2019 and it is expected that recruitment will be completed after 12 months. Each patient will be followed for 12 months and implant loading and data will be collected during this time period. Hence, the end of the study is planned to be November 2021.

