#### 3.7.3 Withdrawal criteria

The Investigator must withdraw any patient from the study in the case of:

- No control and test implants received/ placed at visit 2
- No control and test implant (one of each) available that qualify as study implants (implant is
  assessed as primary stable (as defined in Section 7.2.3) at surgery, the abutment torque is
  at least 15 Ncm at surgery and the implant site fulfills the eligibility criteria, see Section 3.3
  for further details), in 2 different quadrants.

The Investigator may withdraw any patient from the study in the case of:

- Non-compliance with the protocol
- · Failure to attend the follow-up visits
- SAE or AE, which in the opinion of the Investigator prevents the patient's further participation in the study.
- Subject requires surgical treatment during the course of the study in the region of the mouth being evaluated in the study

Any patient may withdraw from the study any time without prejudice and will be offered an alternative treatment related to their dental condition. Patients will be advised of the need for the prescribed follow-up visits for their ongoing care, well-being, and collection of any safety data.

The patient withdrawal will be documented on a Study Termination eCRF page and must include the reason for the patient withdrawal. Withdrawn patients will be replaced in case the recruitment is still ongoing. As soon as recruitment is completed withdrawn patients will not be replaced.

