**Table 3: Visit Days and Windows** 

Visit #	Visit Name	Visit Day and Window
Visit 1	Screening	Up to 10 weeks before implant placement
Visit 2	Implant placement, sampling (baseline)	Day 0
Visit 3	Sampling, suture removal	1 week (+/-1 days)
Visit 4	Sampling	2 weeks (+/-2 days)
Visit 5	Sampling	4 weeks (+/-3 days)
Visit 6	Sampling, final impression	8 weeks (+/-5 days)
Visit 7	Loading	10 weeks (+/- 10 days)
Visit 8	6-month FU	6 months (+/-2 week) after loading
Visit 9	12-month FU	12 months (+/-3 weeks) after loading

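### Section 9.4: enrolling 60 patients for a 20% dropout does not preserve the 51 pairs behind the 92.4% power; without replacement it leaves 48 pairs and 91.0%

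*Combined protocol and SAP*

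**What the plan says.** Section 9.4 sets up a paired non-inferiority comparison of marginal bone loss 12 months after loading. After listing the assumed means, standard deviations and correlation, it concludes: "then with a sample size of 51 patients (51 pairs, a pair within a patient), the study will have a power of 92.4" per cent. The section ends with the enrolment figure: "60 patients will be enrolled in order to take into account a 20% dropout rate". It shows no step from 51 to 60.

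Three other places bear on how many pairs will be available:

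- **Replacement.** Section 3.7.3: "Withdrawn patients will be replaced in case the recruitment is still ongoing. As soon as recruitment is completed withdrawn patients will not be replaced". Screening failures are also replaced (section 11.3.6).
- **Timeline.** Section 3.6: "The first patient was enrolled in the study in October 2019 and it is expected that recruitment will be completed after 12 months". Table 3 puts the last visit at "12 months (+/-3 weeks) after loading", with loading planned 10 weeks (plus or minus 10 days) after surgery.
- **Analysis set.** Section 9.3: "The primary effectiveness analysis will be based on the PP population". Section 9.1 rules out imputation of missing primary outcomes.

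**The concern.** A sample-size section should let the reader go from patients enrolled, through expected loss, to pairs analysed and the power they give. Here the last step fails. Applying the stated dropout rate to the stated enrolment does not return the number of pairs to which the stated power belongs.

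Because the primary analysis is per protocol and nothing is imputed, each lost patient removes one pair. If the planned 20% loss occurs, the reader is left unsure whether the sponsor expects 51 pairs or 48, and so which power figure describes the trial. What is at stake is the accuracy of that statement; the trial's ability to answer its question is not in doubt on this ground.

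**Working it through.** **Inputs, all from section 9.4**

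- One-sided test: "the alpha (one tailed) is set to 0.05".
- Margin: "a non-inferiority margin of 20% of the acceptable clinical standard was chosen, which amounts to 0.1mm".
- Assumed bone loss: SLA 0.46 mm (SD 0.20), SLActive 0.43 mm (SD 0.22).
- Within-patient correlation: 0.0.
- Evaluable pairs: 51. Enrolment: 60. Dropout: 20%.

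**Step 1: reproduce the stated power.**

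- True difference = 0.43 − 0.46 = −0.03 mm.
- Distance to the margin = 0.10 − (−0.03) = 0.13 mm.
- SD of the paired difference at correlation 0 = √(0.20² + 0.22²) = √0.0884 = 0.2973 mm.
- Noncentrality = (0.13 / 0.2973) × √n.
- Power = probability that a noncentral t variable with n − 1 degrees of freedom exceeds the 95th percentile of the central t.

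With n = 51 this gives 0.9244, so the plan's 92.4% is reproduced.

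**Step 2: apply the stated dropout to the stated enrolment.**

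- 20% of 60 = 12 patients lost, and 60 − 12 = **48 pairs**, three fewer than 51.
- To keep 51 pairs after 20% loss: 51 / 0.80 = 63.75, so **64 patients** (63 × 0.80 = 50.4 falls short).
- Loss at which 60 patients leave 51 pairs: 1 − 51/60 = **15%**, or 9 patients.
- Inflating upward instead, 51 × 1.20 = 61.2, does not give 60 either.

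**Step 3: power at the resulting number of pairs, same formula and inputs.**

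| Evaluable pairs | Power |
|---|---|
| 51 | 92.4% |
| 50 | 92.0% |
| 49 | 91.5% |
| 48 | 91.0% |
| 47 | 90.5% |

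At 48 pairs the difference from the stated figure is 92.4 − 91.0 = 1.4 points. Power remains at or above 90% down to 47 pairs.

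**Step 4: can replacement close the gap on the planned timeline?** Time from surgery to the 12-month visit:

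- Nominal: 70 + 365.25 = 435.25 days, about 14.3 months.
- Earliest edge of both windows: (70 − 10) + (365.25 − 21) = 404.25 days, about 13.3 months.

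Recruitment is expected to last 12 months. Even the first patient's 12-month visit therefore falls after recruitment is due to close, and a loss at that visit cannot be replaced. Earlier withdrawals can be replaced while recruitment is open. With 12 patients lost, 3 replacements who complete the study would restore 48 + 3 = 51 pairs.

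**Side check, an assumption outside the plan.** Section 9.4 uses a correlation of 0.0. At 48 pairs, an assumed within-patient correlation of 0.05 gives 92.2%, 0.06 gives 92.4% and 0.10 gives 93.3%. A small positive correlation would offset the loss.

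**The case against.** The strongest reply is that 48 pairs follows only if nobody is replaced, and the protocol does provide for replacement. Patients without a qualifying pair of study implants at surgery must be withdrawn (section 3.7.3), and those early losses can be made good while recruitment is open. Only three successful replacements are needed. The documents do not say how the 20% divides between early and late loss, so the timeline argument shows that late losses cannot be recovered, but not that the gap will remain.

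This stands in part. It makes the 48-pair figure conditional, and the condition must be stated with it. It does not rescue section 9.4 as written: the section does not mention replacement, replacement stops when recruitment closes, and no document says that the 20% is net of replaced patients.

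It can also be said that the matter has no practical consequence. Section 9.4 sets no target power, does not call 51 a minimum, and power at 48 pairs is still 91.0%. That is correct and limits the point to a minor one. A further uncertainty may matter more than the three pairs in dispute: the per-protocol set also excludes patients who lose a study implant and those with major deviations, including a study implant not loaded at the loading visit (sections 9.3 and 11.4.1). No rate is given for these, so their effect cannot be calculated.

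**Conclusion.** The inconsistency is real and minor. The 92.4% belongs to 51 pairs. At the sponsor's own dropout rate, 60 patients without replacement give 48 pairs and 91.0% power, which is 1.4 points lower. The stated pairs and power hold only if net loss is at most 9 of 60 patients (15%).

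This rests on the inputs of section 9.4 and on a paired t-test, which reproduces the plan's figure; the repeated measures model foreseen in section 9.2 may behave slightly differently. It also assumes that the 20% is the loss of evaluable pairs after any replacement. The documents do not confirm that reading.

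**What to change.** Restate the end of section 9.4 and leave enrolment at 60. For example:

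> With 60 patients and a 20% loss that is not replaced (see section 3.7.3), 48 evaluable pairs remain and power is 91.0%. If no more than 9 of the 60 patients (15%) are lost, at least 51 pairs remain and power is at least 92.4%.

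The cross-reference is needed so that the no-replacement scenario is not read as contradicting the replacement rule in section 3.7.3.

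The sponsor should also confirm two things in the same place:

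1. whether the 20% is counted before or after replacement;
2. whether it covers every exclusion from the per-protocol set in section 9.3, or only patients who leave the study.

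The cost is one or two sentences, with no change to enrolment, design or analysis.
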